7.1.2 Rechallenge

In case of temporary discontinuation, subjects should be placed back on study treatment within 3 weeks of the scheduled interruption, unless otherwise discussed with the Sponsor (see Section 6.3). The subjects should be closely monitored for any signs of AEs.

7.2 Subject Discontinuation/Withdrawal from the Study

- A subject may withdraw from the study at any time at his/her own request or may be withdrawn at any time at the discretion of the investigator for safety, behavioural, compliance, or administrative reasons.
- If the subject withdraws consent for disclosure of future information, the Sponsor may retain and continue to use any data collected before such a withdrawal of consent.
- If a subject withdraws from the study, he/she may request destruction of any samples taken and not tested, and the investigator must document this in the study center study records.
- See SoA table ([Table 1](#) in Section 1.3) for data to be collected at the time of study discontinuation and follow-up and for any further evaluations that need to be completed.

7.3 Lost to Follow-up

A subject will be considered lost to follow-up if he or she repeatedly fails to return for scheduled visits and is unable to be contacted by the study center.

The following actions must be taken if a subject fails to return to the clinic for a required study visit:

- The study center must attempt to contact the subject and reschedule the missed visit as soon as possible and counsel the subject on the importance of maintaining the assigned visit schedule and ascertain whether or not the subject wishes to and/or should continue in the study.
- Before a subject is deemed lost to follow-up, the investigator or designee must make every effort to regain contact with the subject (where possible, 3 telephone calls and, if necessary, a certified letter to the subject's last known mailing address or local equivalent methods). These contact attempts should be documented in the subject's medical record.
- Should the subject continue to be unreachable, he/she will be considered to have withdrawn from the study.

8.0 STUDY ASSESSMENTS AND PROCEDURES

A written informed consent will be obtained from the subjects prior to any assessments. Screening assessments will be performed according to the SoA. At the enrolment, demographic information and medical history will be collected. Subsequent study procedures and their timing are also summarised in the SoA ([Table 1](#) in Section 1.3).

- Protocol waivers or exemptions are not allowed for this study.
- Adherence to the study design requirements, including those specified in the SoA, is essential and required for study conduct.
- All screening evaluations must be completed and reviewed to confirm that potential subjects meet all eligibility criteria. The investigator will maintain a screening log to record details of all subjects screened and to confirm eligibility or record reasons for screening failure, as applicable.
- Procedures conducted as part of the subject's routine clinical management (eg, blood count) and obtained before signing of the informed consent form (ICF) may be utilised for Screening or baseline purposes provided the procedures met the protocol-specified criteria and were performed within the time frame defined in the SoA.

8.1 Efficacy Assessments

Tumour imaging is strongly preferred to be acquired by CT scan. For the abdomen and pelvis, contrast-enhanced magnetic resonance imaging (MRI) may be used when CT with iodinated contrast is contraindicated, or when mandated by local practice. Magnetic resonance imaging scan is the strongly preferred modality for imaging the brain. The same imaging technique regarding modality, ideally the same scanner, and the use of contrast should be used in a subject throughout the study to optimise the reproducibility of the assessment of existing and new tumour burden and improve the accuracy of the assessment of response or progression based on imaging. Imaging should include the chest, abdomen, and pelvis.

Tumour assessments will be conducted at time points stipulated in the SoA ([Table 1](#)) based on RECIST 1.1. Initial tumour imaging at screening must be performed within 28 days prior to the date of treatment allocation. The site study team must review screening images to confirm the subject has measurable disease per RECIST 1.1. The first on-study imaging assessment should be performed at 6 weeks (42 days \pm 3 days) from the date of start of treatment. Subsequent tumour imaging should be performed every 6 weeks (42 days \pm 3 days) or more frequently if clinically indicated. After 24 weeks (168 days \pm 7 days), subjects who remain on treatment will have imaging performed every 9 weeks (63 days \pm 7 days). Imaging timing should follow calendar days and should not be adjusted for delays in cycle starts. Imaging should continue to be performed until disease progression is identified and confirmed by the investigator (iRECIST), the start of new anticancer treatment, withdrawal of consent, or death, whichever occurs first.

In case of iUPD, a confirmatory CT scan should be done between 4 to 6 weeks after the iUPD scan depending on the clinical status of the subject and extent of progression. If this interval is 6 weeks after iUPD, this coincides with the next scheduled assessment in the first 24 weeks of the study. If disease progression is not confirmed and treatment continues, tumour imaging should resume at the next scheduled timepoint ensuring an interval between imaging of at least 6 weeks.

For subjects who show evidence of radiological PD by RECIST 1.1 as determined by the investigator, the investigator will decide whether to continue a subject on study treatment until repeat imaging is obtained (using iRECIST for subject management; see [Table 6](#)).

Table 6 Imaging and Treatment after First Radiologic Evidence of Progressive Disease

	Clinically Stable		Clinically Unstable	
	Imaging	Treatment	Imaging	Treatment
First radiologic evidence of PD by RECIST 1.1	Repeat imaging at 4 to 6 weeks to confirm PD.	May continue study treatment at the investigator's discretion while awaiting confirmatory tumour imaging by site by iRECIST.	Repeat imaging at 4 to 6 weeks to confirm PD per the investigator's discretion only.	Discontinue treatment
Repeat tumour imaging confirms PD (iCPD) by iRECIST the per investigator's assessment	No additional imaging required.	Discontinue treatment (exception is possible upon consultation with the Sponsor).	No additional imaging required.	Not applicable
Repeat tumour imaging shows iUPD by iRECIST per the investigator's assessment	Repeat imaging at 4 to 6 weeks to confirm PD. May occur at next regularly scheduled imaging visit.	Continue study treatment at the investigator's discretion.	Repeat imaging at 4 to 6 weeks to confirm PD per investigator's discretion only.	Discontinue treatment

	Clinically Stable		Clinically Unstable	
	Imaging	Treatment	Imaging	Treatment
Repeat tumour imaging shows iSD, iPR, or iCR by iRECIST per the investigator's assessment.	Continue regularly scheduled imaging assessments.	Continue study treatment at the investigator's discretion.	Continue regularly scheduled imaging assessments.	May restart study treatment if condition has improved and/or clinically stable per the investigator's discretion. Next tumour imaging should occur according to the regular imaging schedule.

Abbreviations: iCPD = iRECIST confirmed progressive disease; iCR = iRECIST complete response; iRECIST = modified Response Evaluation Criteria in Solid Tumours 1.1 for immune-based therapeutics; iSD = iRECIST stable disease; iUPD = iRECIST unconfirmed progressive disease; PD = progressive disease; RECIST 1.1 = Response Evaluation Criteria in Solid Tumours 1.1.; VOP=verification of progression

Objective response rate based on best overall response (all time points) using RECIST 1.1 will be the primary efficacy endpoint. RECIST 1.1 will be used as the primary measure for assessment of tumour response, date of disease progression, and as a basis for all protocol guidelines related to disease status except for discontinuation of study treatment. Given the interval of 6 weeks between tumour imaging in the first 24 weeks, there is no requirement to confirm objective response within 4 weeks.

The hepatic lesion that is the site of BO-112 IT administration, if measurable must be included as a target lesion to ensure that any direct effect of the injection is recorded. This lesion(s) will be identified as the site of injection and will also be reported separately.

iRECIST is based on the RECIST 1.1 but adapted to account for the unique tumour response seen with immunotherapeutic drugs. iRECIST will be used by the investigator to make treatment decisions. When clinically stable, subjects should not be discontinued until progression is confirmed by the investigator, according to the rules outlined in [Appendix 1](#). This allowance to continue treatment despite initial radiologic PD takes into account the observation that some subjects can have a transient tumour flare in the first few months after the start of immunotherapy, and then experience subsequent disease response. This data will be captured in the clinical database.

For the assessments of secondary efficacies or clinical activity of the combination therapy in terms of tumour burden and response, following parameters will be determined from CT scan results:

- Disease control rate comprising best response for CR, PR as well as stable disease (SD) lasting at least 12 weeks using RECIST 1.1

- Objective response rate based on best overall response (all time points) using RECIST modified for immune-based therapies (iRECIST)
- Disease control rate comprising best response for CR, PR as well as SD lasting at least 12 weeks using iRECIST
- Duration of response
- PFS
- Overall survival rate 6 months

Exploratory efficacy: Immune cell profile of the TME in injected and noninjected lesions and genomic analysis of the TME will be done on tumour biopsy samples. See Section 8.8 for further details.

8.2 Safety Assessments

Planned time points for all safety assessments are provided in the SoA ([Table 1](#)).

8.2.1 ECOG Performance Status

Eastern Cooperative Oncology Group performance status will be measured in a 0 to 5 scale (See [Appendix 8](#)) at time points stipulated in SoA ([Table 1](#)).

8.2.2 Physical Examinations

Physical examination will be performed at time points stipulated in SoA ([Table 1](#)).

- A full physical examination will include, assessments of the skin, cardiovascular, respiratory, gastrointestinal, musculoskeletal and neurological systems. Body weight will also be measured and recorded.
- A brief physical examination will include examination of any system that had abnormality at previous visits or reported by subjects, as well as assessments of the lungs and abdomen (liver and spleen).
- Investigators should pay special attention to clinical signs related to previous serious illnesses.

8.2.3 Vital Signs

Vital signs will be measured at time points stipulated in SoA ([Table 1](#)).

- temperature, pulse rate and blood pressure will be assessed.
- Blood pressure and pulse rate measurements will be assessed with a completely automated device. Manual techniques will be used only if an automated device is not available.
- Blood pressure and pulse measurements should be preceded by at least 5 minutes of rest for the subject in a quiet setting without distractions (eg, television, cell phones).
- Vital signs (to be taken before blood collection for laboratory tests) will consist of 1 pulse rate and 3 blood pressure measurements (3 consecutive blood pressure readings will be recorded at

intervals of at least 1 minute). The average of the 3 blood pressure readings will be recorded on the eCRF.

8.2.4 **Electrocardiograms**

Electrocardiogram (ECG) will be performed at time points stipulated in SoA ([Table 1](#)).

- Single 12-lead ECG will be obtained as outlined in the SoA (see [Table 1](#) in Section 1.3) using an ECG machine that automatically calculates the heart rate and measures PR, QRS, QT, and QTc intervals. Refer to Section [7.0](#) for QTc withdrawal criteria and any additional QTc readings that may be necessary.

8.2.5 **Clinical Safety Laboratory Assessments**

A complete list of clinical laboratory tests is provided in [Appendix 3](#). Blood and urine samples will be collected at time points stipulated in the SoA ([Table 1](#)) and sent to local laboratories as appropriate.

- Safety laboratory assessments will include standard haematology, chemistry, hepatic function, CRP, renal function and coagulation parameters, pregnancy tests and thyroid tests.
- The investigator must review the laboratory report, document this review, and record any clinically relevant changes occurring during the study in the AE section of the eCRF. The laboratory reports must be filed with the source documents. Clinically significant abnormal laboratory findings are those that are not associated with the underlying disease, unless judged by the investigator to be more severe than expected for the subject's condition.
- All laboratory tests with values considered clinically significantly abnormal during participation in the study or within 28 days after the last dose of study treatment should be repeated until the values return to normal or baseline or are no longer considered clinically significant by the investigator or Medical Monitor.
 - If such values do not return to normal/baseline within a period of time judged reasonable by the investigator, the aetiology should be identified, and the Sponsor notified.
 - All protocol-required laboratory assessments, as defined in [Appendix 3](#), must be conducted in accordance with the laboratory manual and the SoA.
 - If laboratory values from non-protocol specified laboratory assessments performed at the institution's local laboratory require a change in subject management or are considered clinically significant by the investigator (eg, SAE or AE or dose modification), then the results must be recorded in the eCRF.

8.3 **Adverse Events**

The definitions of an AE or SAE can be found in [Appendix 4](#).

Adverse events will be reported by the subject (or, when appropriate, by a caregiver, surrogate, or the participant's legally authorised representative).

The investigator and any designees are responsible for detecting, documenting, and recording events that meet the definition of an AE or SAE and remain responsible for following up AEs that are serious, considered related to the study treatment or study procedures, or that caused the subject to discontinue the study treatment or the study (see Section 7.0).

8.3.1 Time Period and Frequency for Collecting AE and SAE Information

- All AEs or ECIs (Events of Clinical Interest) from the time of treatment start through 30 days following cessation of study treatment must be reported by the investigator. All AEs will be collected at the time points specified in the SoA (Section 1.3).
- All AEs meeting serious criteria, from the time of treatment start through 90 days following cessation of study treatment, or 30 days following cessation of study treatment if the participant initiates new anticancer therapy, whichever is earlier must be reported by the investigator. All SAEs will be collected at the time points specified in the SoA (Section 1.3).
- All pregnancies and exposure during breastfeeding, from the time of treatment/ allocation through 120 days following cessation of study treatment, or 30 days following cessation of study treatment if the participant initiates new anticancer therapy must be reported by the investigator.

Medical occurrences that begin before the start of study treatment but after obtaining informed consent will be recorded on the medical history/Current Medical Conditions section of the ECRF, not the AE section.

All SAEs will be recorded and reported to the Sponsor or designee within 24 hours, as indicated in [Appendix 4](#). The investigator will submit any updated SAE data to the Sponsor within 24 hours of it being available.

Investigators are not obligated to actively seek AE or SAE after conclusion of the study participation. However, if the investigator learns of any SAE, including a death, at any time after a subject has been discharged from the study, and he/she considers the event to be reasonably related to the study treatment or study participation, the investigator must promptly notify the Sponsor.

The method of recording, evaluating, and assessing causality of AE and SAE and the procedures for completing and transmitting SAE reports are provided in [Appendix 4](#).

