1.3 Schedule of Activities

Table 1 Schedule of Assessments

Treatment Cycle		1		2	3	4	5	6, 8 ... 34	7, 9 ... 35	EOS
Visit	Screening	V1a Baseline	V1b	V2	V3	V4	V5	V6, V8 ... V34 (even numbered visits)	V7, V9 ... V35 (odd numbered visits)	EOS
Day of visit within treatment cycle	Day -28 to Day -1	Day 1	Day 8 ± 2 days	Day 1 ± 2 days	Days 1 ± 2 days	Days 1 ± 2 days	28 days after last treatment ± 3 days			
Study Week		W1	W2	W4	W7	W10	W13	W16, W22 ... W100	W19, W25 ... W103	
Administrative procedures										
Informed consent Form	X									
Inclusion/Exclusion criteria	X									
Demography	X									
Medical history	X									
Safety										
Physical examination ^a	X	X	X	X	X	X	X	X	X	X
Vital signs ^a	X	X	X	X	X	X	X	X	X	X
12-Lead ECG	X	X					X			X
ECOG PS ^a	X	X	X	X	X	X	X	X	X	X
Adverse events ^a		X	X	X	X	X	X	X	X	X
Concomitant medication ^a	X	X	X	X	X	X	X	X	X	X
Coagulation ^b	X	X	X	X	X	X	X	X	X	

Treatment Cycle		1		2	3	4	5	6, 8 ... 34	7, 9 ... 35	EOS
Visit	Screening	V1a Baseline	V1b	V2	V3	V4	V5	V6, V8 ... V34 (even numbered visits)	V7, V9 ... V35 (odd numbered visits)	EOS
Day of visit within treatment cycle	Day -28 to Day -1	Day 1	Day 8 ± 2 days	Day 1 ± 2 days	Days 1 ± 2 days	Days 1 ± 2 days	28 days after last treatment ± 3 days			
Study Week		W1	W2	W4	W7	W10	W13	W16, W22 ... W100	W19, W25 ... W103	
Haematology ^{b, c}	X	X	X	X	X	X	X	X	X	X
Chemistry, CRP ^{b, d}	X	X	X	X	X	X	X	X	X	X
Thyroid function tests ^e		X			X		X		X	X
Pregnancy (for WOBCP only) ^f	X				X		X		X	X
Efficacy										
Tumour Biopsy ^g		X		X						
Tumour burden and response assessment (per RECIST 1.1) ^{h,i}	X				X		X	V7 and V9 then V12, V15, V18, V21, V24, V27, V30, V33		
Pharmacokinetics										
PK blood sample ^j		X								
Study drug administration										
Pembrolizumab		X ^k		X	X	X	X	X	X	
BO-112 ^l	X	X	X	X	X	X	X	X	X	
Abbreviations: AE=adverse events; CRP= C-reactive protein; CT= computed tomography; ECG=electrocardiogram; ECOG PS= Eastern Cooperative Oncology Group Performance Status; EOS=End of Study; PK=Pharmacokinetic; RECIST= response evaluation criteria in solid tumours; SAE=serious adverse events; V=visit; WOBCP=woman of childbearing potential										

Notes:

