- a. Physical examination (full examination at baseline, and brief examination subsequently), ECOG PS, AE recording and concomitant medications recordings will be evaluated every 3 weeks (Q3W) prior to pembrolizumab treatment and prior to BO-112 injection at Week 2. Physical examination will include measurement of body weight. Also, vital signs will be collected on the same visits and temperature, pulse rate, and blood pressure, will be assessed.
- b. Safety laboratory assessments: standard haematology, chemistry, CRP and coagulation parameters (prothrombin time [PT] and activated partial prothrombin time [aPTT]) will be measured prior to pembrolizumab treatment at baseline (V1a), then prior to pembrolizumab treatment at each cycle. Coagulation tests only need to be done if BO-112 is planned to be administered at that visit. If the safety screening labs are done within 5 days prior to V1a, then these labs do not need to be repeated for V1a, and the screening laboratory results for coagulation, haematology and chemistry results will be used for V1a (baseline). Note: safety labs (coagulation, haematology and chemistry) need to be done within 2 weeks of start of treatment.
- c. Haematology assessment will include white blood cell count with differential, platelet counts, red blood cell (RBC) count, haemoglobin, haematocrit, RBC indices (ie, mean corpuscular volume (MCV), mean corpuscular haemoglobin (MCH), % reticulocytes).
- d. Clinical chemistry test will include alanine amino transferase (ALT), aspartate amino transferase (AST), alkaline phosphatase, total bilirubin, blood urea nitrogen (BUN), creatinine, sodium, potassium, calcium, chloride, magnesium, phosphate, bicarbonate, albumin, total protein, and glucose.
- e. Thyroid function (triiodothyronine (T3) or free triiodothyronine (FT3), free thyroxine (FT4) and thyroid stimulating hormone [TSH]) will be measured from blood samples at baseline and every 6 weeks.
- f. Urine pregnancy test will be performed for all WOCBP. If a urine pregnancy test (within 72 hours prior to treatment) is positive or cannot be confirmed as negative, a serum pregnancy test will be required to confirm negative pregnancy.

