The screening period will be from Days -28 to -1, ie, within 4 weeks before the start of the treatment. The screening assessments will be performed according to the Schedule of Assessments (SoA; see Section 1.3). Baseline will be at Week 1.

Study Treatment Period

The study treatment period will comprise 3-week cycles. Treatment and assessment schedules vary somewhat over time and are described in detail in Section 6.0 and section 1.3, respectively. The overall study duration could be extended up to 2 years (ie, Visit 35 plus the end of study [EOS]

visit 28 days after last dose of treatment) depending on the achieved clinical benefit. Individual subject study duration will depend on maintenance of clinical benefit and tolerability and is expected to range from 2 to 12 months, although the study foresees 2 years of treatment.

The study treatment will consist of BO-112 IT injections in combination with IV infusion of pembrolizumab infusions and will be administered in 3-week cycles for both Cohort A and Cohort B subjects.

BO-112 (1 mg) and pembrolizumab (200 mg) will be administered as described in Section 6.1.

Blood samples will be collected for haematology, renal function and hepatic functions tests, C-reactive protein (CRP), and coagulation parameters measurements, prior to any study drug administration at any visit for the first 13 weeks and subsequently every 6 weeks.

Urine pregnancy test will be performed for all women of childbearing potential (WOCBP). If a urine pregnancy test (within 72 hours prior to treatment) is positive or cannot be confirmed as negative, a serum pregnancy test will be required to confirm negative pregnancy.

Tumour biopsies will be performed at baseline (Week 1) prior to first administration of BO-112, on the “to be injected (injected)” lesions and optionally, of a non-hepatic “not to be injected (noninjected)” lesion. On the Week 4, 1 post-treatment biopsy of the injected lesion and if applicable, of the noninjected lesion will be performed.

Physical examinations (full at baseline and brief at subsequent visits), Eastern Oncology Cooperative Group (ECOG) performance status³⁷, AEs, concomitant medications will be evaluated at screening and each visit (ie, at Week 1, Week 2, and Q3W week thereafter) prior to the pembrolizumab treatment.

End of Study

An EOS visit will be performed for all subjects at 4 weeks after last administered study treatment.

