9.3.2 Safety Analyses

All safety analyses will be performed on the safety analysis set separately for each cohort. In Cohort A, subjects who are dMMR will be evaluated together with pMMR subjects.

Treatment-emergent adverse events are defined as AEs that first occurred or worsened in severity after the first administration of study treatment and prior to 30 days after the last administration of study treatment.

Adverse events will be coded using the Medical Dictionary for Regulatory Activities (MedDRA). Numbers of TEAEs and incidence rates will be tabulated by preferred term and system organ class.

Treatment-emergent AEs of any grade, TEAEs with severity \geq Grade 3 (NCI-CTCAE v 5.0), TEAEs (any grade) by relationship to study treatment, TEAEs related (probable, possible or unknown causality) to study treatment with severity \geq Grade 3 (NCI-CTCAE v 5.0) SAEs, TEAEs leading to death, and TEAEs leading to discontinuation of study treatment will be tabulated for the number and proportion of subjects. Additionally, treatment tolerability will be determined by the number of study discontinuations due to treatment-related TEAEs. Commonly occurring TEAEs,

ie, those that occur in 5% or more of the subjects in either treatment group, will be summarised using descriptive statistics.

All laboratory test results, vital signs measurements, ECG results, weight, and body mass index will be summarised using descriptive statistics at each visit for raw numbers and change from baseline. The incidence of treatment-emergent abnormal laboratory, vital sign, and ECG values will also be summarised using descriptive statistics.

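### SAEs are to be collected to day 90 at scheduled time points, but the schedule ends at EOS (day 28 ± 3), leaving 59 to 65 of the 90 days without a scheduled SAE contact

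*Combined protocol and SAP*

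**What the plan says.** Section 8.3.1 sets two reporting windows. For AEs and events of clinical interest it runs "from the time of treatment start through 30 days following cessation of study treatment must be reported by the investigator". For serious events it covers "All AEs meeting serious criteria, from the time of treatment start through 90 days following cessation of study treatment", shortened to day 30 if the subject starts new anticancer therapy. The section says how SAEs are to be gathered: "All SAEs will be collected at the time points specified in the SoA". It says the same for AEs. It then adds: "Investigators are not obligated to actively seek AE or SAE after conclusion of the study participation".

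The last column of Table 1 (section 1.3) is EOS, timed at "28 days after last treatment ± 3 days". The AE row is marked there, and no visit or call follows. Section 4.1 agrees on the timing: "An EOS visit will be performed for all subjects at 4 weeks after last administered study treatment". Appendix 7 also places EOS 28 days after the last dose.

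For analysis, section 9.3.2 counts as treatment-emergent those AEs that begin or worsen after the first dose and "prior to 30 days after the last administration of study treatment".

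**The concern.** The SAE obligation runs to day 90, but the mechanism named for meeting it stops at about day 28. Section 8.3.2 prefers open verbal questioning of the subject as the way to detect events, and that needs a contact. Sections 7.1.1 and 7.2 send the reader to Table 1 for follow-up data, but Table 1 has no follow-up column. Section 4.4 ends the study at the last visit or last scheduled procedure of the last subject, so the trial can formally close before that subject's 90 days are over.

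What is at stake is late serious toxicity. Sections 2.2.2 and 6.3.1 say that immune-related events may appear several months after the last pembrolizumab dose, and 6.3.1 says that the part BO-112 plays in causing or potentiating them is not known. Earlier experience of injecting liver lesions, as reported in 2.2.2, is 3 subjects (2 in Part 1 and 1 in Part 2). SAEs are a tabulated output under 9.3.2. If sites differ in how hard they look after EOS, the count depends partly on site practice.

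**Working it through.** The plan gives no figure of its own to reproduce. The check is a count of days after the last treatment.

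**Inputs**
- Permitted EOS days: 28 ± 3, so days 25 to 31 (Table 1).
- End of SAE window: day 90, or day 30 with new anticancer therapy (8.3.1).
- End of AE reporting window: day 30 (8.3.1).
- TEAE window: before day 30, so the last full day is day 29 (9.3.2).
- Scheduled contacts after EOS: none (Table 1).

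**Formulas**, with E the day of EOS
- SAE gap = 90 − E; share of the window = (90 − E)/90
- AE reporting gap = max(0, 30 − E)
- TEAE gap = max(0, 29 − E)

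| EOS day | SAE gap (days) | Share of 90 days | AE gap (days) | TEAE gap (days) |
|---|---|---|---|---|
| 25 | 65 | 72.2% | 5 | 4 |
| 26 | 64 | 71.1% | 4 | 3 |
| 27 | 63 | 70.0% | 3 | 2 |
| 28 (nominal) | 62 | 68.9% | 2 | 1 |
| 29 | 61 | 67.8% | 1 | 0 |
| 30 | 60 | 66.7% | 0 | 0 |
| 31 | 59 | 65.6% | 0 | 0 |

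**Reading the table**
- No permitted EOS day closes the SAE gap. It is 59 to 65 days for any subject who does not start new therapy. If new therapy starts, the window ends at day 30 and the gap falls to the 0 to 5 days of the AE column.
- EOS falls short of the AE reporting window on 5 of the 7 permitted days (25 to 29), and covers it on 2 (30 and 31).
- EOS falls short of the TEAE window on 4 of the 7 days (25 to 28), by 1 day at the nominal visit and by 4 at most.

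**The case against.** The sponsor can fairly say that 8.3.1 makes SAEs to day 90 reportable whatever their cause, and that the sentence on not seeking events concerns active search, not reporting. That stands. A reader might infer that the 90-day duty is cancelled after EOS, or survives only for related events, but the text does not say so. The relatedness condition belongs to the separate provision for SAEs learned of at any time after discharge. What is missing is active ascertainment.

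Nor does the plan say that participation ends at EOS for everyone. Section 4.4 links completion to the EOS visit only for subjects who stop for confirmed progression. For others the end of participation is undefined, so sites may read the sentence differently. That is a reason to clarify it.

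There may also be contact after EOS. Section 8.1 continues imaging until confirmed progression, new treatment, withdrawal of consent or death. Section 8.3.3 requires proactive follow-up once an event has been reported. The overall survival analysis in 9.3.1 needs 6-month status. None of these is a Table 1 time point after EOS, and none provides for asking about new SAEs. They soften the gap for some subjects without closing it.

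On the AE side, a reader might infer that no visit reaches the end of the 30-day window. EOS on day 30 or 31 does reach it, so coverage is uncertain, not absent.

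**Conclusion.** The inconsistency between 8.3.1 and Table 1 is real for SAEs and should be resolved. Followed as written, the plan leaves 59 to 65 of the 90 days (66% to 72%) without a scheduled SAE contact for subjects who start no new anticancer therapy. Late serious events can be under-counted. The documents give no rate for such events after EOS, so the size of the under-count cannot be estimated, and a statement that the counts will certainly be biased would go too far.

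The AE shortfall is minor. It would be tempting to conclude that the primary safety endpoint (subjects with related TEAEs of Grade 3 or higher) is seriously compromised. The documents do not support that. The uncovered part of the TEAE window is 1 day at nominal EOS and 4 at most, against an expected individual study duration of 2 to 12 months (4.1), and the long SAE gap lies almost wholly outside that window.

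This conclusion assumes that Table 1 is the complete schedule of contacts, as 8.3.1 implies, and that EOS is held within its permitted window.

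**What to change.** 1. In Table 1, add a telephone SAE contact at day 90 after the last treatment, or at day 30 if new anticancer therapy has started. Record the start date of any new therapy at the call, so that it is clear which window applied.
2. In Table 1, add a day-30 AE telephone check for subjects whose EOS is held before day 30. It can double as the day-30 SAE contact.
3. In 8.3.1, limit the sentence on not actively seeking events to the time after the 30- and 90-day windows have closed.

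Keep EOS at 28 days. Moving it to day 30 or later would also mean changing section 4.1, the 28-day laboratory window in 8.2.5 and the pregnancy-testing text in Appendix 7. The calls avoid that.

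The cost is one or two short calls per subject by existing site staff, plus the Table 1 additions and one wording change in an amendment. The 120-day pregnancy reporting window in 8.3.1 likewise has no scheduled contact after EOS and could be reconciled at the same time.
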